11.9 Pregnancy in the Clinical Study

Pregnancy is not reportable as an AE; however, complications may be reportable and will be decided on a case-by-case basis. An eCRF will be utilized to capture all pregnancy-related and lactating information.

[figure not shown]
12 ANALYSIS PLAN

12.1 Subject Evaluability

Final subject evaluability must be determined prior to breaking the code for masked treatment assignment and locking the database, based upon the Deviations and Evaluability Plan. Subjects will be randomized for bilateral treatment in a 1:1 ratio to receive the investigational product.

12.2 Analysis Sets

The primary analysis set for effectiveness will be the All-Implanted Analysis Set (AAS). The AAS will include all eyes with successful study IOL implantation and with at least one postoperative visit.

All eyes with attempted study IOL implantation (successful or aborted after contact with the eye) will be considered evaluable for the safety analysis set (SAS).

The primary analysis set for effectiveness will be the AAS, [REDACTED]
[REDACTED]
[REDACTED]
[REDACTED]

12.3 Demographic and Baseline Characteristics

Demographic and baseline characteristics will be summarized by treatment group and overall. Counts and percentages will be presented for categorical variables such as sex, age group (< 65 years and \geq 65 years), race, and ethnicity. N, mean, standard deviation, median,

minimum, and maximum will be presented for continuous variables that are collected at baseline such as age, eye biometry, [REDACTED] binocular VA, refractive errors, and IOP.

12.4 Effectiveness Analyses

12.4.1 Analysis of Primary Effectiveness Endpoint

The primary objective of this study is to demonstrate noninferiority of the Clareon/Clareon Toric IOLs to the Eyhance/Eyhance Toric IOLs in binocular BCDVA at 3 months postoperative. The primary effectiveness endpoint is, mean binocular BCDVA under bright lightning conditions at 4 m at 3 months postoperative.

12.4.2 Statistical Hypotheses

The null (H_0) and alternative (H_1) hypotheses to be evaluated in support of the primary noninferiority objective are:

$$H_0: \mu_{Test} - \mu_{Comparator} \geq \Delta$$

$$H_1: \mu_{Test} - \mu_{Comparator} < \Delta$$

Where, Δ refers to the noninferiority margin, set at 0.1 logMAR, and μ_{Test} , $\mu_{Comparator}$ refers to the mean values of binocular BCDVA for the test (Clareon/ Clareon Toric) and comparator (Eyhance/Eyhance Toric) IOLs respectively at 3 months post implantation.

12.4.3 Analysis Methods

The noninferiority objective as well as the corresponding hypothesis will be evaluated using a t-test of noninferiority assuming equal variances, if the equality of variance is not rejected, or assuming unequal variance when the equality of variance is rejected based on Levene's test. The null hypothesis is rejected, that is the noninferiority is claimed, if the upper bound of the one-sided 95% confidence interval does not exceeds the noninferiority margin of 0.1 logMAR. Primary analysis will be based on AAS. [REDACTED]

[figure not shown]
Standard descriptive statistics will be presented for the primary endpoint where the number of subjects/eyes, mean, median, standard deviation, minimum, maximum, and 95% confidence intervals will be reported based on AAS [REDACTED] at 3 months visit.

[figure not shown]
12.4.4 Analysis of Secondary Effectiveness Endpoints

There are no secondary effectiveness endpoints in this study.

12.4.5 Statistical Hypotheses

No hypothesis testing of the secondary effectiveness endpoint(s) is planned.

12.5 Handling of Missing Data

There will be no imputation for missing data.

12.6 Safety Analyses

The safety endpoints are:

- All adverse events (ocular and non-ocular, serious and non-serious)
- SSI
- Device Deficiencies
- IOL observations
- IOL position change (tilt and decentration)

- PCO
- Posterior capsulotomy
- Surgical problems
- Other surgical procedures
- Slit lamp examination
- Dilated fundus examination
- IOP

There are no safety hypotheses for this study. For all safety measures, descriptive statistics generated will be based upon the type of variable. For categorical variables summary statistics will include sample size, number in category, and % in each category. For continuous variables, number of subjects/eyes, mean, median, standard deviation, minimum, and maximum will be reported.

All adverse events occurring from the time a subject sign informed consent to study exit will be accounted for in the reporting. Safety analyses will be conducted using the safety analysis set on a treatment-emergent basis. Descriptive summaries (counts and percentages) and listings will be presented. Individual subject listings will be provided for AEs that occur after signing informed consent but prior to exposure to IP.

13 DATA HANDLING AND ADMINISTRATIVE REQUIREMENTS

13.1 Subject Confidentiality

The Investigator must ensure that the subject's identity is kept confidential throughout the course of the study. In particular, the investigator must keep an enrollment log with confidential identifying information that corresponds to the subject numbers and initials of each study participant. The study sponsor may collect a copy of the enrollment log without any directly identifying subject information.

The study sponsor may share patient-level data collected in this trial with qualified researchers to help facilitate product development or enhancements in research that is not directly related to the study objectives. The Informed Consent explains this to the study subject.

13.2 Completion of Source Documents and Case Report Forms

The nature and location of all source documents will be identified to ensure that original data required to complete the CRFs exist and are accessible for verification by the site monitor, and all discrepancies shall be appropriately documented via the query resolution process. Site monitors are appointed by the study sponsor and are independent of study site staff.

If electronic records are maintained, the method of verification must be determined in advance of starting the study.

At a minimum, source documents include the following information for each subject:

- Subject identification (name, sex, race/ethnicity)

- Documentation of subject eligibility
- Date of informed consent
- Dates of visits
- Documentation that protocol specific procedures were performed
- Results of study parameters, as required by the protocol
- IP dispensing records
- Documentation of AEs and other safety parameters (if applicable)
- Records regarding medical histories and the use of concomitant therapies prior to and during the study
- Date of study completion and reason for early discontinuation, if applicable

It is required that the author of an entry in the source documents be identifiable. Direct access to source documentation (medical records) must be allowed for the purpose of verifying that the data recorded on the CRF are consistent with the original source data.

Only designated individuals at the site will complete the CRFs. The CRFs must be completed at regular intervals following the clinical study visit schedule. It is expected that all data reported have corresponding entries in the source documents. The principal investigator is responsible for reviewing and certifying that the CRFs are accurate and complete. The only subject identifiers recorded on the CRFs will be subject number, and subject demographic information.

13.3 Data Review and Clarifications

A review of CRF data to the subject's source data will be completed by the site monitor to ensure completeness and accuracy. After the CRFs have been completed, additional data clarifications and/or additions may be needed as a result of the data cleaning process. Data clarifications are documented and are part of each subject's CRF.

13.4 Sponsor and Monitoring Responsibilities

The Study Sponsor will designate a monitor to conduct the appropriate site visits at the appropriate intervals according to the study monitoring plan. The clinical investigation will be monitored to ensure that the rights and well-being of the subjects are protected, the reported data are accurate, complete, and verifiable from the source documents, and the study is conducted in compliance with the current approved protocol (and amendments[s], if applicable), with current GCP, and with applicable regulatory requirements

The site may not screen subjects or perform the informed consent process on any subject until it receives a notification from an appropriate Study Sponsor representative that the site may commence conducting study activities. Monitoring will be conducted periodically while the clinical study is ongoing. Monitoring methods may include site visits, telephone, written and email correspondence. Close-out visits will take place after the last visit of the last subject at the site.

A Coordinating Investigator may be identified by the Study Sponsor to review and endorse the final study report. In cases where a Coordinating Investigator is engaged, the Study Sponsor will select the Coordinating Investigator based upon their experience, qualifications, active study participation, and their willingness and availability to take on this role.

13.5 Regulatory Documentation and Records Retention

The investigator is required to maintain up-to-date, complete regulatory documentation as indicated by the study sponsor and the investigator's files will be reviewed as part of the ongoing study monitoring. Financial information is to be kept separately.

Additionally, the investigator must keep study records and source documents consistent with the terms of the clinical study agreement with the study sponsor. If the investigator retires, relocates, or for any other reason withdraws from responsibility of keeping the study records, then the study sponsor must be notified, and suitable arrangements made for retention of study records and source documents needed to comply with national and international regulations.

13.6 Quality Assurance and Quality Control

The study sponsor will secure agreement from all involved parties to ensure direct access to all study related sites, source data and documents, and reports for the purpose of monitoring and auditing by the study sponsor, and inspection by domestic and foreign regulatory authorities. Quality control will be applied to each stage of data handling to ensure that all data are reliable and have been processed correctly. Agreements made by the study sponsor with the investigator/institution and any other parties involved in the clinical study will be provided in writing as part of the protocol or as a separate agreement.

14 ETHICS

Investigations are conducted in compliance with Good Clinical Practices; international and national regulations, laws and guidelines; the conditions of approval imposed by reviewing

IRBs/IECs or regulatory authorities; and in accordance with the ethical medical research principles outlined in the Declaration of Helsinki.

- The SOPs of the study sponsor and contract research organizations participating in the conduct of the clinical study and all other applicable regulations shall apply.
- Notifications and timelines for reporting protocol deviations should be based upon applicable Ethics Committee requirements.

The investigator must ensure that all personnel involved in the conduct of the study are qualified to perform their assigned responsibilities through relevant education, training, and experience. The investigator and all clinical study staff must conduct the clinical study in compliance with the protocol. The investigator is not allowed to deviate from the protocol except to protect the rights, safety, and well-being of human subjects under emergency circumstances. Emergency deviations may proceed without prior approval of the sponsor and the IRB/EC, but shall be documented and reported to the sponsor and the IRB/EC as soon as possible. Deviations from this protocol, regulatory requirements, and/or GCP must be recorded and reported to the Sponsor prior to database lock. If needed, corrective and preventive action should be identified, implemented, and documented within the study records. Failure to implement identified corrective and preventative actions may result in site closure by the sponsor. Use of waivers to deviate from the clinical protocol is prohibited.

Before clinical study initiation, this protocol, the informed consent form any other written information given to subjects, and any advertisements planned for subject recruitment must be approved by an IRB/IEC. The investigator must provide documentation of the IRB/IEC approval to the study sponsor. The approval must be dated and must identify the applicable protocol, amendments (if any), informed consent form, assent form (if any), all applicable recruiting materials, written information for subject, and subject compensation programs. The IRB/IEC must be provided with a copy of any periodic safety updates, and all other information as required by local regulation and/or the IRB/IEC. Any additional requirements imposed by the EC or regulatory authority shall be followed, if appropriate. At the end of the study, the investigator must notify the IRB/IEC about the study's completion. The IRB/IEC also must be notified if the study is terminated prematurely. Finally, the investigator must report to the IRB/IEC on the progress of the study at intervals stipulated by the IRB/IEC.

Voluntary informed consent must be obtained in writing from every subject and/or legal representative, as applicable. The obtaining of consent shall be documented before any procedure specific to the clinical investigation is applied to the subject.

The investigator must have a defined process for obtaining the required consent. Specifically, the investigator, or their delegate, must explain the clinical study to each potential subject and the subject must indicate voluntary consent by signing and dating the approved informed consent form. The subject must be provided an opportunity to ask questions of the investigator, and if required by local regulation, other qualified personnel. The investigator must provide the subject with a copy of the consent form written in a language the subject understands. The consent document must meet all applicable local laws and provide subjects with information regarding the purpose, procedures, requirements, and restrictions of the study, along with any known risks and potential benefits associated with the IP and the study, the available compensation, and the established provisions for maintaining confidentiality of personal, protected health information. Subjects will be told about the voluntary nature of participation in the study and must be provided with contact information for the appropriate individuals should questions or concerns arise during the study. The subject also must be told that their records may be accessed by appropriate authorities and sponsor-designated personnel. The investigator must keep the original, signed copy of the consent (file in subject's medical records) and must provide a duplicate copy to each subject according to local regulations.

The study sponsor assures that the key design elements of this protocol will be registered on www.clinicaltrials.gov if required by current regulations and, if applicable, other public databases as required by local country regulations. In addition, results of this study will be made publicly available on www.clinicaltrials.gov regardless of outcome if required by current regulations and, if applicable, in other public databases as required by local country regulations.

Clareon Toric vs Eyhance Toric

STUDY ID:
ILS241-P002

STATISTICAL ANALYSIS PLAN

[figure not shown]
Version 2, 14 Nov 2023

ClinicalTrials.gov ID:

NCT05481125

Statistical Analysis Plan for ILS241-P002
Title: Clareon Toric vs Eyhance Toric

[figure not shown]

This is version 2.0 of the Statistical Analysis Plan based on Version 4.0 of the study protocol.

Executive Summary:

Key Objectives:

The primary objective of this study is to demonstrate noninferiority of the Clareon/Clareon Toric intraocular lens (IOL) to the Eyhance/Eyhance Toric IOLs in binocular best corrected distance visual acuity (BCDVA) under bright lighting conditions at 3 months postoperative.

[figure not shown]
Decision Criteria for Study Success:

The study will be considered successful if the data indicate a noninferior visual acuity for the Clareon/Clareon Toric IOLs compared to the Eyhance/Eyhance Toric IOLs. Study success will be concluded if the upper bound of the one-sided 95% confidence interval does not exceed the noninferiority margin of 0.1 logMAR for the BCDVA at 3 months postoperative for Clareon/Clareon Toric IOLs vs the Eyhance/Eyhance Toric IOLs. Primary analysis will be based on All-Implanted Analysis Set (AAS). [REDACTED]

Table of Contents

Statistical Analysis Plan for ILS241-P002	1
Table of Contents	3
List of Tables.....	5
List of Figures	5
1 STUDY OBJECTIVES AND DESIGN	6
1.1 Study Objectives.....	6
1.2 Study Description	6
1.3 Randomization.....	7
1.4 Masking.....	8
█	█
2 ANALYSIS SETS	9
2.1 Effectiveness Analysis Sets	9
2.2 Safety Analysis Set.....	9
3 SUBJECT CHARACTERISTICS AND STUDY CONDUCT SUMMARIES	10
3.1 Subject Disposition and Study Conduct.....	10
3.2 Demographics.....	11
3.3 Medical History and Concomitant Medications.....	12
3.4 Baseline Eye Biometry	12
3.5 Baseline Visual Acuity and MRSE.....	13
3.6 Surgical Summary	13
4 EFFECTIVENESS ANALYSIS STRATEGY.....	14
4.1 Effectiveness Endpoints	14
4.2 Effectiveness Hypotheses	15
4.2.1 Primary Effectiveness Hypothesis.....	15
█	█
4.3 Statistical Methods for Effectiveness Analyses.....	17
4.3.1 Primary Effectiveness Analysis.....	17
█	█
█	█
█	█
█	█

[figure not shown]

1 STUDY OBJECTIVES AND DESIGN

1.1 Study Objectives

Primary effectiveness objective:

To demonstrate noninferiority of the Clareon/Clareon Toric IOLs to the Eyhance/Eyhance Toric IOLs in binocular BCDVA at 3 months postoperative. The corresponding endpoint is the mean difference in binocular BCDVA under bright lighting conditions at 4 m at 3 months postoperative.

Secondary Objective:

Not applicable. There are no secondary objectives in this study.

1.2 Study Description

[figure not shown]
This is a prospective, multi-center, randomized, double-masked (subject and VA assessor), parallel group, postmarket study.

The study will enroll approximately 185 subjects who will be randomized to bilateral implantation of either Clareon/Clareon Toric IOLs or Eyhance/Eyhance Toric IOLs. The study will include adults 22 years of age and older, diagnosed with cataracts in both eyes, and planned bilateral cataract removal by routine small incision phacoemulsification surgery. Patients are required to have at least 1 eye planned for cataract surgery with a toric IOL. The fellow eye may be planned for toric or non-toric IOL implantation. A total of up to 7 scheduled visits (4 postoperative visits) are planned over a period of 5 months.

An overview of study design is depicted in Figure 1.1.

The schedule of visits is included as Table 10-1 in the appendix.

Figure 1-1 Study Diagram

* Option for the 2nd eye to be operated on the same day as the 1st eye. It is recommended that Visit 00 (1st eye surgery) occur within 0 to 30 calendar days after the Preoperative Visit (Visit 0). If not occurring on the same day, the 2nd eye IOL implantation should be conducted within 14 days after 1st eye implantation.

1.3 Randomization

Subjects will be randomized in a 1:1 manner to receive treatment bilaterally with either Clareon/Clareon Toric IOLs or Eyhance/Eyhance Toric IOLs, respectively. Subjects will be block randomized by investigational site.

Only after signing the ICF, a subject will be assigned a subject number by the electronic data capture (EDC) system. If all eligibility criteria are met and the subject desires to continue in the study, randomization will proceed.

[figure not shown]
It is recommended that randomization occur within 14 days prior to 1st eye surgery. A randomization list will be generated using a validated system that automates the random assignment of treatment arms to randomization numbers in the specified ratio. Subjects will be assigned treatment according to the randomization list uploaded in the EDC system. The randomization list will be generated and maintained by the study sponsor.

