
Key exclusion criteria (See Section 8.2 for a complete list of exclusion criteria)
	
• Any disease or pathology, other than cataract, that (in the investigator’s opinion) may reduce the potential BCDVA to a level worse than 0.2 logMAR• Clinically significant (in the investigator’s opinion) corneal pathology (epithelial, stromal, endothelial), dry-eye or ocular surface disease that would adversely affect a) the biometry measures and/or toric calculations and b) the visual outcome. This includes, but is not limited, to old significant corneal scars (including Salzmann’s nodular degeneration), corneal irregularity (including dry eye syndrome), active or inactive keratitis with compromise of the refractive capability of the cornea, keratoconjunctivitis sicca with compromise of visual function, active keratouveitis, endothelial dystrophy (Fuch’s and non-guttate), keratoconus, etc.• History of previous intraocular or corneal surgery (including iridotomy and laser-assisted in situ keratomileusis (LASIK)).• Any other planned ocular surgical procedures including but not limited to limbal relaxing incision (LRI), astigmatic keratotomy, LASIK, and retinal laser treatment within the study time frame.

**Data analysis and
sample size
justification**

[figure not shown]
Analysis sets:

The all-implanted analysis set (AAS) will include all eyes with successful study IOL implantation and with at least one postoperative visit.

All eyes with attempted study IOL implantation (successful or aborted after contact with the eye) will be considered evaluable for the safety analysis set (SAS).

The primary analysis set for effectiveness will be the AAS.

Analysis:

The null and alternative hypotheses to be evaluated for the primary noninferiority objectives are as stated below:

$$H_0: \mu_{Test} - \mu_{Comparator} \geq \Delta$$

$$H_1: \mu_{Test} - \mu_{Comparator} < \Delta$$

[figure not shown]
where, Δ refers to the noninferiority margin, set at 0.1 logMAR, and μ_{Test} , $\mu_{Control}$ refers to the mean values of binocular BCDVA

[REDACTED] [REDACTED]
[REDACTED] [REDACTED]
[REDACTED] at 3 months post-implantation.

The primary effectiveness [REDACTED] will be evaluated with a *t*-test of noninferiority assuming equal variances, unless a Levene's test of equal variances is significant at the 5% level. In that case, the hypothesis test will be conducted with a *t*-test of noninferiority allowing for unequal variances.

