8 STUDY POPULATION

The study population consists of adults 22 years of age or older, diagnosed with binocular cataract who require bilateral cataract extraction by phacoemulsification.

We aim to enroll (consent) approximately 185 subjects in approximately 10 sites in the US with a target of approximately 23-31 subjects per site. Each site should contribute no more than 25% of the total enrolled study sample size. Site-specific targets may vary based upon individual site capabilities. The estimated time needed to recruit subjects for the study is approximately 5 months, however, unanticipated circumstances may shorten or lengthen this time and would not require amendment of this protocol.

Assuming a 10% screening failure rate and 16% dropout rate, data from approximately 140 subjects (70 subjects per group) will be available for statistical analysis at 3 months.

Enrollment projections are as follows:

- Approximately 185 subjects to be enrolled (sign consent) (a 10% screen failure rate is estimated)
- Approximately 168 subjects randomized (approximately 84 per group) to be bilaterally implanted (a 16% dropout rate is estimated)

- Minimum 140 subjects (approximately 70 subjects per group) to successfully complete the final study visit (Visit 3A)

Check all entry criteria at Screening/Visit 0 and at both surgical visits (Visit 00, Visit 00A). If a subject is excluded following enrollment and prior to 1st eye surgery (IOL does not come in contact with the eye), the subject should be discontinued from participation in the study.

Refer to Section 8.4 Reasons for Discontinuation (During Surgery) for further details.

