8.1 Inclusion Criteria

Subjects eligible for inclusion in this study must fulfill **all** of the following criteria:

1.	Adults 22 years of age and older (at the time of screening) diagnosed with cataracts in both eyes.
2.	Able to comprehend and willing to sign an IRB/IEC approved informed consent.
3.	Planned bilateral cataract removal by routine small incision phacoemulsification surgery.
4.	Planned implantation of either test or comparator IOL (per randomization) from the following model numbers: CNW0T3, CNW0T4, CNW0T5, CNW0T6 or DIU150, DIU225, DIU300, DIU375 in at least one eye with approximately 1.00 – 3.00 D of preoperative corneal astigmatism.
5.	Predicted postoperative astigmatism of $\leq 0.5D$ in both operative eyes based on a Toric calculator.
6.	Calculated IOL power between 10.0 D and 25.0 D when targeted for emmetropia or first minus residual refraction.
7.	Potential postoperative best corrected distance visual acuity of 0.2 logMAR or better in both eyes based on the Investigator’s expert medical opinion (Note: Subjects with any pathology that could reduce visual potential should not be enrolled in this study).
8.	Pupil constriction with a penlight to ≤ 3.5 mm.
9.	Pupil able to dilate to > 6.0 mm.

10.	Clear intraocular media other than cataract.
11.	Willing and able to complete all required postoperative visits.

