9.2 Other Medical Device or Medication Specified for Use During the Study

Systane preservative free drops are required to be used bilaterally prior to both corneal tomography and biometry measures.

The Clareon/Clareon Toric IOLs must be delivered by the Clareon Monarch IV Delivery System.

Each study surgeon should follow his/her routine cataract procedure for all study surgeries.

Femtosecond laser-assisted cataract surgery (FLACS) is permitted for Investigators that currently use this procedure as part of their standard of care for cataract surgery, however, it is **NOT** permitted on primary incisions.

FLACS may **ONLY** be used for the following:

- Capsulorhexis
- Lens fragmentation

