4.3.1 Primary Effectiveness Analysis

[figure not shown]
The noninferiority hypothesis of the primary endpoint will be evaluated based on the difference in means (Clareon/Clareon Toric *minus* Eyhance/Eyhance Toric) and the associated 95% upper confidence limit using a two-sample t-test. Using Levene's test, equality of variance between the two treatments will be assessed. If the test for equality of variance is not rejected, equal variance can be assumed. The null hypothesis is rejected, and noninferiority is claimed, if the upper bound of the one-sided 95% confidence interval does not exceed the noninferiority margin of 0.1 logMAR. The primary analysis will be based on AAS. [REDACTED]

[figure not shown]
The mean difference between treatments, the associated standard error, and 95% upper confidence limit will be presented for the primary endpoint based on AAS [REDACTED] at the 3-month visit.

[figure not shown]

[figure not shown]

[figure not shown]

[figure not shown]

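### Randomisation is blocked by site, but the visible primary t-test has no site term, so its upper limit is somewhat too wide if sites differ

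*SAP*

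**What the plan says.** SAP 1.3 sets 1:1 allocation and adds "Subjects will be block randomized by investigational site". The block size is not visible. Protocol 9.3 describes 1:1 allocation from a list and does not mention site blocking.

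The primary test is given in three places, none with a site term in the visible text:

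- SAP 4.3.1 uses the difference in means "and the associated 95% upper confidence limit using a two-sample t-test", with Levene's test deciding whether equal variance is assumed.
- Protocol 12.4.3 has the objective "evaluated using a t-test of noninferiority assuming equal variances, if the equality of variance is not rejected".
- The Protocol 3 summary switches, if Levene's test is significant at 5%, to a "test of noninferiority allowing for unequal variances".

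Noninferiority is claimed if the one-sided 95% upper limit does not exceed 0.1 logMAR.

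On sites, Protocol 8 plans recruitment "in approximately 10 sites in the US with a target of approximately 23-31 subjects per site" and adds "Each site should contribute no more than 25% of the total enrolled study sample size". Protocol 9.2 says "Each study surgeon should follow his/her routine cataract procedure for all study surgeries". Text directly after the primary-analysis paragraphs is blacked out in both documents.

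**The concern.** Blocking within site keeps the arms nearly balanced at each site, so differences between sites largely cancel from the treatment difference. A t-test does not use that balance. It counts between-site variation as noise, and so reports more uncertainty than the design produces.

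The stake is power, not a false claim: the error makes noninferiority harder to show. It is worth raising because the sponsor already randomises on site and can use it in the analysis at little cost.

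The direction is claimed only for additive site effects and for dropout unrelated to arm and outcome. The plan analyses eyes as treated (SAP 2.1), imputes nothing (Protocol 12.5), and takes no binocular acuity from subjects without a second study lens (Protocol 8.4). If missingness depends on arm or outcome, nothing is claimed here.

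**Working it through.** **Planned numbers.** 140 / (1 − 0.16) = 166.7, so 167 randomised against about 168 stated. 168 / (1 − 0.10) = 186.7, so 187 enrolled against about 185 stated. Both agree to rounding. The SD and power behind 70 per group are not visible and cannot be rebuilt.

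**Number of sites.** Protocol 8 gives about 10 sites and also 23 to 31 subjects per site. For 185 enrolled, 185 / 31 = 6.0 and 185 / 23 = 8.0, so 6 to 8 sites; ten sites would give 230 to 310 subjects. Both 7 and 10 sites were therefore examined.

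**Assumptions not in the documents.** Total SD 0.12 logMAR, blocks of 4, additive normal site effects, and a between-site share of variance ρ from 0 to 0.20.

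**Approximation.** With K equal sites, the pooled within-arm variance used by the t-test is about SD² × (1 − ρ/K); a site model leaves SD² × (1 − ρ). Estimating site effects after dropout costs a further 0.7% on the standard error (SE) with ten equal sites, the simulated ratio at ρ = 0 being 0.993. So

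SE ratio (t-test / site model) ≈ 0.993 × √[(1 − ρ/10) / (1 − ρ)]

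- ρ = 0.05: 0.993 × √(0.995/0.95) = 1.016
- ρ = 0.10: 0.993 × √(0.99/0.90) = 1.041
- ρ = 0.20: 0.993 × √(0.98/0.80) = 1.099

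Setting the ratio to 1 gives break-even at ρ ≈ 0.015.

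**Upper limit at ρ = 0.20.** With 168 × 0.84 = 141 analysed, the t-test SE is 0.12 × √(4/141) × √0.98 = 0.0200. The site-model SE is 0.0200 / 1.099 = 0.0182. The gap is 1.656 × 0.0018 = 0.0030 logMAR. SAP 5.3 equates 10 letters with 0.2 logMAR, so this is 0.15 letter against a margin of 5 letters.

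**Simulation.** 168 randomised, 16% random dropout, t-test with the Levene step. Four layouts: 10 equal sites, 10 unequal, 7 equal, 7 unequal, none above 25%. There were 20,000 runs per case for SE and power, and 80,000 for type I error. Ranges are over layouts; power is at a true difference of 0.05.

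| ρ | SE ratio | t-test upper limit minus site model (logMAR) | Type I error, t-test | Power, t-test | Power, site model |
|---|---|---|---|---|---|
| 0 | 0.991–0.996 | −0.0003 to −0.0001 | 0.050–0.052 | 0.792–0.797 | 0.788–0.795 |
| 0.05 | 1.013–1.019 | 0.0004–0.0006 | 0.046–0.048 | 0.795–0.802 | 0.803–0.807 |
| 0.10 | 1.037–1.043 | 0.0012–0.0014 | 0.044–0.045 | 0.803–0.809 | 0.823–0.827 |
| 0.20 | 1.091–1.099 | 0.0027–0.0030 | 0.038–0.039 | 0.814–0.822 | 0.860–0.864 |

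The site model holds type I error at 0.049 to 0.052. At a true difference of 0, power is above 0.999 for both methods.

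**Dependence on SD.** At SD 0.15, power at a true difference of 0.05 is 0.631–0.636 (t-test) vs 0.658–0.662 (site model) for ρ = 0.10, and 0.649–0.650 vs 0.707–0.713 for ρ = 0.20. At SD 0.10 and ρ = 0.10 it is 0.91–0.92 vs 0.92–0.93.

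**Is blocking the cause?** A separate simulation at SD 0.10 compared the t-test SE with the true SD of the t-test's own estimate. The ratio was 1.02, 1.03 and 1.08 at ρ = 0.05, 0.10 and 0.20. With unblocked randomisation at ρ = 0.10 it was 1.00, so the excess comes from blocking that the analysis ignores. Block sizes of 2 and 6 gave 1.03 and 1.02 at ρ = 0.10.

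**The case against.** The t-test is valid under these conditions and errs on the safe side, so preferring a site model is a matter of efficiency. That stands, and it is why the point is optional.

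The effect depends on inputs the documents do not give. Site differences may be very small: acuity is best-corrected, entry requires "Potential postoperative best corrected distance visual acuity of 0.2 logMAR or better in both eyes", and trained masked assessors do the testing. Protocol 7.2 says the lenses were chosen for potential similarity, so a deficit of half the margin is not shown to be a planning scenario. This also stands. Below a share of about 0.01 to 0.02 the site term loses a little precision.

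The 9 to 10% at ρ = 0.20 compares two estimators. Dropout unbalances the blocks, so some site variation returns to the raw difference. Measured against the true variability of its own estimate, the t-test SE is about 8% too wide. The 0.003 logMAR therefore combines overstated SE with a gain in efficiency. The direction is unchanged.

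Finally, a heteroscedasticity-robust HC2 SE is undefined for a site with one analysed subject. This arises in roughly 27 to 28% of runs in the most unequal layout without pooling. A pooling rule removes that case, but pooling itself was not simulated.

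**Conclusion.** The concern holds as an optional improvement. The visible primary test ignores the factor used in randomisation. If sites differ additively, and dropout is unrelated to arm and outcome, its SE and upper limit are somewhat too wide.

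At between-site shares of 0.05, 0.10 and 0.20 the t-test SE exceeds the site-model SE by 1.3–1.9%, 3.7–4.3% and 9.1–9.9%. The practical cost is some power when the test lens is truly somewhat worse; there is no added risk of a false noninferiority claim. At a true difference of 0 and SD 0.12 the conclusion would not change. The finding concerns only the visible primary test.

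**What to change.** In SAP 4.3.1, Protocol 12.4.3 and the protocol summary, make the primary analysis a linear model of 3-month binocular BCDVA with treatment and site. Claim noninferiority on the one-sided 95% upper limit of the adjusted difference against 0.1 logMAR.

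- **Unequal variances.** Use an HC2 SE with t on n − (number of sites) − 1 degrees of freedom, whatever Levene's test shows. With the test arm's within-site SD 1.5 times the comparator's, HC2 type I error was 0.046–0.053. Power at a true difference of 0.05 was 0.628–0.635 (t-test with the Levene rule) vs 0.644–0.650 (HC2) at ρ = 0.10, and 0.651–0.657 vs 0.686–0.694 at ρ = 0.20. Avoid HC3: its SE is 3–4% larger, which cancels the gain up to a share of about 0.10 with ten sites.
- **Small sites.** Before unmasking, fix a pooling rule based on total counts only, for example merging the smallest sites until each unit holds at least one full randomisation block of analysed subjects.
- **Sensitivity analysis.** Keep the current t-test with its Levene rule.

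**Cost.** No new data. The site term uses 6 (7 sites) to 9 (10 sites) of about 139 degrees of freedom. If sites do not differ, the SE rises by 0.4–0.9%, the upper limit by 0.0001–0.0003 logMAR, and power at a true difference of 0.05 is 0.788–0.795 instead of 0.792–0.797. Changing the protocol text needs an amendment under Protocol 4, normally with ethics approval.
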